#### 5.1.1. Pre-Operative Inclusion Criteria

Pre-Operative Inclusion Criteria	
All subjects are required to meet the following inclusion criteria in order to be considered eligible for participation in this trial:
 

1. 18 to 80 years of age;

2. Capable and willing to give informed consent;

3. Acceptable candidate for an elective, non-emergent catheter-based procedure via the common femoral vein(s) using a 6 to 12 Fr inner diameter introducer sheath, with a minimum of 3 and a maximum of 4 femoral venous access sites, and a maximum of 2 access sites/leg;

4. Able and willing to complete a 30 day +/- 7 days follow-up visit;

5. Acceptable candidate for emergent vascular surgery, and/or manual compression of the venous access sites;

6. A total of 50 subjects willing to undergo ultrasound evaluation at the 30 day +/- 7 day visit at select sites.

7. Anticipated prolonged bedrest (5 hours or longer) and / or overnight stay.

-----------------------------------------	----------------------------------------------------------------------------------------------------------------------------------------------------------------------------------------------------------------------------------------------------------------------------------------------------------------------------------------------------------------------------------------------------------------------------------------------------------------------------------------------------------------------------------------------------------------------------------------------------------------------------------------------------------------------------------------------------------------------------------------------------------------------------------------------------------------------------------------------------------------------------------------------------------------------------------------------------------------------------------------

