#### 7.4.4. Intra-Operative Randomization

At the end of the catheter-based procedure, with the procedural sheaths in place and under fluoroscopic visualization, an injection of contrast will be made to assess sheath placement and the anatomy of all venous access sites to verify the intra-operative eligibility criteria prior to randomization. These images should be saved and printed/stored with the subject's study records for monitoring purposes.

- Each venous access site must meet all intra-procedural access site-specific criteria for the subject to be eligible.

Once it has been determined that the subject does not meet any of the general intra-operative exclusion criteria, and that none of the venous access sites meet the specific access site exclusion criteria (i.e., all venous access sites must meet all study criteria for the subject to be eligible), then the subject is eligible for randomization.

- Once randomized, every access site will be closed according to the treatment assignment (i.e., either VVCS or manual compression).
- Study data will be captured for each access site, according to the instructions below.
- ***NOTE: Any subject that is randomized is considered to be enrolled, and all peri-procedural study data must be collected under the Intent to Treat principle regardless of deviations from the assigned treatment. For this reason, it is imperative that randomization is not performed until the case is complete and final eligibility criteria are confirmed.***
- ***If the subject is randomized to Mid-Bore VVCS and it is subsequently discovered that one or more of the access sites is not able to be closed (e.g., complication) apply manual compression to the affected access sites and close all eligible access sites using Mid-Bore VVCS. All study data will still be collected for each access site. See Section 4.2 Withdrawal of Subjects.***

At each investigational site, variable block randomizations will be performed separately by number of venotomy sites via EDC access at the conclusion of the index procedure, while the patient is on the table. Randomization will be stratified by 3 vs. 4 access sites, and there will be a 1:1 randomization ratio for Cardiva Mid-Bore VVCS vs. manual compression for access site closure. Refer to the Manual of Operations for instructions on how to randomize a subject.

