**Documenting Access Site Hemostasis in Both Treatment Arms:**

While performing the procedure, record the following information:

- **P1 TIME:** time of removal of final index procedure device/catheter
- For each access site, record:
  - Access site location, e.g., right/left leg and relative location with respect to 2nd access site, if applicable e.g. proximal/distal, medial/lateral, etc.
  - Final introducer sheath size (inner diameter and length) at time of closure (i.e. after final sheath exchanges)
  - **TX.1 TIME:** time of removal for Mid-Bore VVCS device (treatment arm) or for removal of sheath (control arm)
  - **TX.2 TIME:** time venous hemostasis is achieved
  - Confirm that venous hemostasis is maintained and confirmed at 5 minutes after recorded hemostasis time (TX.2).
  - Document any light manual compression applied for tissue tract ooze.

Note: *For VVCS arm, formation of a hematoma post-sheath removal may indicate a back-wall or secondary venous or arterial puncture. If this situation is suspected, the VVCS should be removed and the subject should be converted to manual compression at that location. Additional access*

 source worksheets and clock/timers will be provided and required by Sponsor

*sites may still be closed with Mid-Bore VVCS, as appropriate.*

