#### **Manual Compression:**

Follow institutional guidelines for ambulation. Check groin immediately post ambulation. Re-check groin after 15 minutes to verify status. Any delays of > 30 minutes beyond institution's standard practice for ambulation that are not related to a medical condition (e.g., pt. is sleeping, no staff available) will be documented, and a Protocol Deviation will be written.

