#### **9.2.2. Effectiveness**

##### **9.2.2.1. Primary Effectiveness (TTA) Analysis**

The primary effectiveness endpoint is time to ambulation (TTA) as defined in Section 7.1. Summary statistics for TTA (mean, standard deviation, median, minimum, and maximum) will be reported for all randomized patients (ITT) and further by the randomization stratification factor

(number of access sites per patient: 3 vs. 4) within each treatment arm. The proportions of Cardiva Mid-Bore VVCS converted to manual compression will also be reported.

The main effectiveness analysis will be based on the mean TTA. The hypotheses are as follows.

- $H_0$ : Cardiva Mid-Bore VVCS mean TTA  $\geq$  manual compression mean TTA
- $H_A$ : Cardiva Mid-Bore VVCS mean TTA  $<$  manual compression mean TTA

An ANCOVA analysis will be performed adjusting for randomization stratification factor, i.e. 3 vs 4 access sites. A 1-sided  $p < 0.025$  by t test favoring the Cardiva Mid-Bore VVCS (i.e. shorter TTA) will be regarded as a successful demonstration of the superiority of the Cardiva Mid-Bore VVCS effectiveness over manual compression.

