### **9.3. Sample Size Justification**

#### Effectiveness

Based on a prior study (RESPECT), mean TTA for manual control is estimated at 7.2 hours. The same mean for Cardiva Mid-Bore VVCS is estimated at 5 hours including an outlier and at 4.3 hours excluding the outlier. With an estimated joint standard deviation of 5.4 hours, the power for reaching a statistically significant difference at 2-sided 0.05 level with a total sample size of 204 (102 per group) is 0.83 including the outlier in the calculation; the same power is 0.97 excluding the outlier.

Safety

For the purpose of sample size/power estimation, we will assume major access site closure complications to be independent between the two limbs of the same subject. Based on clinical experience this is the most likely scenario for these rare events. According to review of the VASCADE arterial VCS RESPECT study, the combined major complication rate by limb is estimated to be 2% for both VVCS and manual compression. With these assumptions, simulations were conducted using the R software for a sample size of 204 each for VVCS and manual compression patients. The power for the Newcombe 2-side 95% confidence upper limit to exclude 5% is approximately 0.88.

In order to evaluate the Newcombe method as an approximation to the proposed analysis method, i.e. bootstrap by patient, systematic comparisons were performed between the upper limit of Newcombe and bootstrap confidence intervals. Complication rates of 0% – 3% were selected for comparison, as this range is expected to cover great majority of the actual cases. The results are presented in the following table.

 IDE G100246

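### The primary TTA model omits end-of-case clock time (P1), a recorded pre-randomization value that plausibly predicts TTA; the test is valid without it and the likely gain is small

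*Combined protocol and SAP*

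**What the plan says.** Section 9.2.2.1 compares mean TTA between arms by ANCOVA at 1-sided 0.025. Its covariate statement reads in full: "An ANCOVA analysis will be performed adjusting for randomization stratification factor, i.e. 3 vs 4 access sites". No other covariate is named.

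P1 is defined in section 7.4.5 as "time of removal of final index procedure device/catheter" and appears in Table 4 as an hh:mm time for every subject. Section 19.2 places removal of the last procedural device before any sheath exchange. Section 7.4.4 says "it is imperative that randomization is not performed until the case is complete". P1 is therefore fixed before assignment.

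Three provisions bear on whether hour of day could affect TTA:

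- Section 5.1.1, criterion 7, requires "Anticipated prolonged bedrest (5 hours or longer) and / or overnight stay".
- Section 7.4.6 leaves control ambulation to institutional guidelines. Control delays of more than 30 minutes beyond local practice "that are not related to a medical condition (e.g., pt. is sleeping, no staff available) will be documented" as deviations.
- Section 7.4.6 sets a 2 to 2.5 hour bed-rest window for the device arm and names the same two non-medical causes of delay.

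Section 9.3 plans on "mean TTA for manual control is estimated at 7.2 hours", a device mean of 5 hours (4.3 without an outlier) and an SD of 5.4 hours. It allows for no covariate gain.

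**The concern.** With 5 to 7 hours of bed rest, a case ending at 10:00 is due to walk between 15:00 and 17:00. One ending at 18:00 is due between 23:00 and 01:00, and may not walk until morning. If that happens, part of the spread in TTA, mainly among controls, follows from when the case ended. That was known before randomization, and the planned model leaves it in the residual.

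What is at stake is precision and protection against chance imbalance in late cases. Under ITT (section 9.1.1) delayed subjects stay in the analysis, so a few extra late cases in one arm move that arm's mean. Adjustment for P1 carries most weight if it is fixed beforehand; added after an imbalance is seen, it would look data-driven.

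**Working it through.** **1. The plan's own power.** Inputs from section 9.3: difference 7.2 − 5.0 = 2.2 h (7.2 − 4.3 = 2.9 h without the outlier), SD 5.4 h, 102 per arm, 2-sided 0.05.

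- Standard error = 5.4 × √(2/102) = 0.756 h.
- 2.2/0.756 = 2.909, and Φ(2.909 − 1.960) = 0.829. The plan says "power for reaching a statistically significant difference at 2-sided 0.05 level with a total sample size of 204 (102 per group) is 0.83".
- 2.9/0.756 = 3.835, and Φ(3.835 − 1.960) = 0.970. The plan says "the same power is 0.97 excluding the outlier".
- The noncentral t gives 0.825 and 0.968; these are the baselines below.

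Both figures reproduce without P1, so omitting it leaves no shortfall against plan.

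**2. How much P1 could explain.** The documents give no figure, so this step rests on an assumed model:

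- P1 is uniform from 09:00 to 19:00.
- Device TTA is uniform from 2.2 to 2.7 h; control bed rest is uniform from 5 to 7 h.
- A control due to walk after 22:00 is held, with probability p, until a time uniform from 06:00 to 08:00.
- The short interval between P1 and final sheath removal is ignored.

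About 30% of controls fall due after 22:00. The model was simulated with 400,000 subjects per arm. R² is the within-arm variance removed by one common P1 slope. The interval narrows by 1 − √(1 − R²). The last two columns put the same P1 effect on the planning variance: share = R² × SD² / 5.4², then power at 2.2 h with SD = 5.4 × √(1 − share) and 200 df.

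| p | pooled SD (h) | R² | interval narrower by | share of 5.4² | power at 2.2 h |
|---|---|---|---|---|---|
| 0.10 | 1.01 | 1.6% | 0.8% | 0.06% | 0.825 |
| 0.25 | 1.49 | 4.8% | 2.4% | 0.4% | 0.827 |
| 0.50 | 1.97 | 10.7% | 5.5% | 1.4% | 0.831 |
| 0.75 | 2.30 | 17.7% | 9.3% | 3.2% | 0.837 |
| 1.00 | 2.53 | 26.2% | 14.1% | 5.8% | 0.847 |

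Worked for p = 1: 0.262 × 2.53² = 1.68 h²; 1.68/29.16 = 5.8%; SD 5.24 h; power 0.847. At 2.9 h the same step moves power from 0.968 to 0.976.

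**3. Why the two scales must be kept apart.** At the model's own SDs, unadjusted power for 2.2 h is already about 1.00 (at SD 2.53 h the standard error is 0.354 h and the ratio is 6.2). Where P1 explains a sizeable share of variance, the gain is a narrower interval rather than power.

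**4. What may lie behind 5.4 h.** In Table 2 the VASCADE arm has N = 275, mean 3.8, SD 5.1 and maximum 78.0 h. The sum of squares is 274 × 5.1² = 7,127. The single maximum supplies (78.0 − 3.8)² × 275/274 = 5,526, or 78%. Without it the SD is √(1,601/273) = 2.4 h. Section 9.3 uses other means than Table 2, so this is only indicative, but end-of-case time would not explain a 78-hour value.

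**5. Validity with P1 added.** In 3,000 simulated null trials (P1 uniform 10:00-20:00, half of those due after 22:00 held overnight in both arms), rejection was 0.027 without P1 and 0.026 with it. The nominal level is 0.025 and the simulation error about 0.003.

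**The case against.** The strongest reply is that nothing is broken. The model adjusts for the factor that it stratifies on, the test is valid, and the planned power never relied on P1. That stands.

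The mechanism is also inferred. No section says that hour of day decides when a patient walks, and parts of section 7.4.6 point the other way: staff are to make every effort to keep the timelines, device bed rest is fixed, and long non-medical delays are deviations in both arms. Frequent overnight holding would mean either many deviations or local practice that itself defers walking. That stands as a limit on the size, and p = 0.10 above shows a negligible gain. It does not remove the case for adjusting, since the protocol itself foresees such delays and ITT keeps the delayed subjects in.

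The effect may be an evening threshold acting mainly in controls, which one common slope captures only in part. That limits the gain; with 1:1 randomization the adjusted contrast still targets the mean difference.

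Site has more direct support as a source of variation, because blocks run within site (section 7.4.4) and control ambulation is institution-specific. That is fair, but it is a separate choice: site would capture differences between institutions, and P1 differences by hour within them.

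A reader might apply the model's 5-26% directly to the 5.4 h SD and infer power of about 0.90 or more, or the equivalent of many extra subjects. The documents do not support that: those percentages arise only at SDs of 1.5-2.5 h.

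**Conclusion.** The point holds as a small, nearly free improvement in precision. The primary model leaves out a recorded pre-randomization value with a plausible link to the outcome. Under the assumed overnight-holding model the interval narrows by about 2-14% if the trial's SD is 1.5-2.5 h. If the SD is the planned 5.4 h, power at 2.2 h rises from 0.825 to about 0.83-0.85 at most. All of this rests on assumed case-end times, bed-rest times and holding probabilities.

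A reader might also infer that the plan is underpowered or the test biased without P1. Neither follows: both stated powers reproduce, and randomization with the planned ANCOVA gives a valid comparison.

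**What to change.** In section 9.2.2.1, before any unblinded TTA data are seen, specify the primary model as TTA = treatment + access sites (3 vs 4) + P1 clock time, with P1 continuous (hours since midnight on the procedure day) and one common slope. Use a robust standard error, because the P1 effect may differ by arm. Keep the 1-sided 0.025 test and report the model without P1 as a sensitivity analysis.

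Fill a missing P1 by simple covariate imputation that ignores treatment arm, such as the mean over both arms. P0 should not stand in for it: the two times differ by the whole procedure and cannot share a scale.

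The cost is a few lines of text and one degree of freedom, with no new data, subjects or change in patient care. The downside is little gain if next-morning walking proves rare.

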#### 9.2.2.2 Secondary Effectiveness Endpoints Analyses

Secondary effectiveness endpoints include total post procedure time (TPPT), time to discharge eligibility (TTDE), and time to discharge (TTD).

TTH will be compared between the two study arms by the bootstrap method with patient as the re-sampling unit as opposed to access site, as within patient TTH times may be correlated. Otherwise the analysis will be similar to those for the primary safety analysis described in 8.2.3, and the proposed TTH non-inferiority margin will be 5 minutes for VVCS as compared to manual compression.

Lastly, time to closure eligibility (TTCE), procedure success, and proportions of device success (VVCS only, by access site) will be descriptively summarized without hypothesis testing.

#### 9.2.3. Safety

##### Primary Safety Analysis

The primary safety analysis will be based on the 30-day limb incidence rate of combined major access site closure complications (see 7.3). Both the combined rate and individual complication incidence rates will be reported by treatment received as described in 8.1.2.

The statistical hypotheses are as follows:

- $H_0$ : Cardiva Mid-Bore VVCS rate – manual compression rate  $\geq 5\%$
- $H_A$ : Cardiva Mid-Bore VVCS rate – manual compression rate  $< 5\%$

A 2-sided 95% confidence interval will be constructed by the bootstrap re-sampling method, with patient as the sampling unit as opposed to the limb, for the VVCS – manual compression

major complication rate difference. This is to account for an unlikely correlation between two limbs of a patient with respect to major closure complications. One million bootstrap resampling simulations will be performed. For each simulation, stratified sampling with replacement (by randomization stratification factor) will be performed separately for the two study arms and the VVCS – manual compression (MC) major complication rate difference will be recorded. With one million simulations, a data distribution will be generated for the VVCS – MC major complication rate difference. With patient as the sampling unit, any data structure (independent or correlated) between the same patient's two limbs is preserved in this data distribution. If the 97.5th percentile of the distribution, i.e. the upper limit of the 2-sided 95% confidence interval for the VVCS – MC difference, is <5%, then the null hypothesis of a ≥5% higher VVCS complication rate will be rejected at a 2-sided 0.05 significance level. In this case the VVCS major complications rate will be considered non-inferior to that of the manual compression.

As an example to illustrate the actual study results required in order to accomplish this goal, assume the two limbs within each patient to be independent (highly likely) and a 2% (4/204) major complication rate is observed for the MC control treatment. The observed VVCS major complication rate must be ≤ 3% (6/204) in order for the 95% confidence upper limit for the difference to be <5%. This confidence interval calculation is based on Newcombe's method derived from Wilson scores. (*Ref: Newcombe RG, Interval Estimation for the Difference between Independent Proportions: Comparison of Eleven Methods, Statistics in Medicine, 17, 8 73-890, 1998*).

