**VASCADE Arterial VCS RESPECT Study Overview:**

The RESPECT trial was aimed at evaluating safety and efficacy of the extravascular, bioabsorbable closure system, VASCADE VCS. This was a multicenter, randomized comparison of VASCADE versus Manual Compression (MC) in Diagnostic (Dx) and Interventional (Ix) patients undergoing femoral access through 6/7 F introducer sheaths. Subjects were randomized 2:1, VASCADE versus MC.

Endpoints included:

- Time to Hemostasis (TTH)
- Time to Ambulation (TTA)
- Discharge Eligibility (TTDE)
- Time to Discharge (TTD)
- Device and Procedure Success
- Major and Minor Complications

A total of 420 patients were enrolled (211 Dx, 209 Ix). Mean age was 62 years with 29% of subjects being female. For Ix patients, 77%/69% (VASCADE/MC) received bivalirudin and 8%/3% received GP IIb/IIIa inhibitors. Patients were followed for 30 days.

The RESPECT trial demonstrated that the extravascular VASCADE closure device was safe and effective compared to manual compression in patients in whom 6 and 7 French femoral access was employed in Dx and Ix procedures. Despite high percentage of Bivalirudin use (77%), there were zero major access site related complications in either arm.

In addition, the use of VASCADE demonstrated a statistically significant reduction in minor access site related complications and significantly shortened TTH, TTA, and time to discharge eligibility (TTDE) when compared to MC.

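### The planned bootstrap gives an arm with no major complications zero variance, so the primary safety interval is invalid at very low event counts (exactly 0% to 0% at 0 v 0)

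*Combined protocol and SAP*

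**What the plan says.** Section 9.2.3 (Primary Safety Analysis) compares the 30-day major complication rate per limb against a 5-point margin. On the interval it says: "A 2-sided 95% confidence interval will be constructed by the bootstrap re-sampling method, with patient as the sampling unit as opposed to the limb". On the mechanics: "One million bootstrap resampling simulations will be performed", and "stratified sampling with replacement (by randomization stratification factor) will be performed separately for the two study arms". The decision uses one number. The condition begins "If the 97.5th percentile of the distribution, i.e. the upper limit of the 2-sided 95% confidence interval for the VVCS – MC difference"; if that value is below 5%, "then the null hypothesis of a ≥5% higher VVCS complication rate will be rejected at a 2-sided 0.05 significance level".

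Newcombe's interval appears in 9.2.3 only as a worked example and in 9.3 only for power. Section 9.3 plans on a low but non-zero rate: "the combined major complication rate by limb is estimated to be 2% for both VVCS and manual compression". It attributes this to RESPECT, about which Section 1.1 says "there were zero major access site related complications in either arm"; Table 1 in Section 1.4 shows 0 of 275 and 0 of 142.

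Table 5 compares Newcombe and bootstrap upper limits for observed rates of 0% to 3%, because "this range is expected to cover great majority of the actual cases". No section says what to report when an arm has no events.

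**The concern.** The bootstrap takes its variance only from the observed events. If an arm has none, every resample of that arm is zero. More resamples, stratification and patient-level sampling cannot change that. With no events in either arm, the primary safety interval has zero width and would be the same with 10 patients or 10,000. It then says nothing about how much excess risk has been excluded, which is the purpose of a non-inferiority interval.

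At stake are a primary safety result reported without uncertainty and, at a few counts, a verdict that depends on the interval method. Table 5 does not reveal the first problem, because 0 v 0 is the one combination of 0, 2, 4 and 6 events that it leaves out.

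**Working it through.** **Inputs.** 204 subjects randomized 1:1 (Section 4.2) gives 102 per arm. Eligibility requires 3 or 4 access sites with at most 2 per leg, so both limbs are always used: 102 × 2 = 204 limbs per arm. The margin is 5 points and the planning rate is 2% in both arms (9.2.3 and 9.3). Limbs are taken as independent, as in 9.3.

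**Reproducing the plan's figures.** Enumerating Binomial(204, 0.02) counts in both arms, the Newcombe upper limit is below 5% with probability 0.877, against the stated 0.88. (9.3 calls the 204 per arm patients, but the figure reproduces with 204 limbs; 102 per arm gives 0.48 and 408 gives 0.996.) All 15 Newcombe limits and all 42 bootstrap limits in Table 5 also reproduce to three decimals.

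**Formulas.** Write p1 = x1/204 for VVCS, p2 = x2/204 for manual compression and d = p1 - p2.
- Bootstrap, with all events in different patients: each arm's resampled count is Binomial(102, x/102). The difference in counts is divided by 204, and the limits are its 2.5th and 97.5th percentiles. Stratification is ignored here; it has no effect on an arm with x = 0.
- Newcombe, with Wilson limits (l, u) per arm: lower = d - √[(p1 - l1)² + (u2 - p2)²]; upper = d + √[(u1 - p1)² + (p2 - l2)²].

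**0 v 0.** Binomial(102, 0) is always 0, so the bootstrap interval is 0% to 0%. The Wilson upper limit for 0/204 is z²/(n + z²) = 3.84/207.84 = 1.85%, so Newcombe gives ±1.85%.

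**4 v 0.** The percentiles of Binomial(102, 4/102) are 1 and 8, so the bootstrap gives 1/204 = +0.5% to 8/204 = +3.9%. The Wilson limits for 4/204 are 0.77% and 4.93%. Newcombe's lower limit is 1.96 - √(1.20² + 1.85²) = -0.2%, and its upper limit is 4.9%.

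**5 v 0.** The 97.5th percentile of Binomial(102, 5/102) is 10, so the bootstrap upper limit is 10/204 = 4.9% and non-inferiority is met. Newcombe's upper limit is 5.6% and it is not met. With x2 = 0, p2 - l2 = 0, so the manual compression arm adds nothing to Newcombe's upper limit either. This gap comes from the bootstrap's short upper tail in the VVCS arm at small counts. The missing variance of a zero arm shows in the lower limit at x v 0, in the upper limit at 0 v x, and in both limits at 0 v 0.

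**Coverage of the nominal 95% interval (exact enumeration).**

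| True rates, VVCS v MC | Bootstrap | Newcombe |
|---|---|---|
| 0.5% v 0.25% | 63% | 99.9% |
| 1% v 0.5% | 86% | 99% |
| 2% v 1% | 92% | 98% |
| 0.5% v 0.5% | 98.6% | 99.7% |
| 1% v 1% | 95.9% | 98.3% |
| 2% v 2% | 96% | 96% |

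Most of the shortfall in the first two rows comes from a VVCS arm with no events, because the upper limit is then at most 0. At 0.5% that has probability (1 - 0.005)^204 = 36%, and at 1% it is 13%.

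**How often zeros occur, with the same true rate in both arms.** P(0 v 0) = (1 - p)^408.

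| True rate | P(0 v 0) | P(at least one arm with zero) |
|---|---|---|
| 2% | 0.03% | 3.2% |
| 1% | 1.7% | 24% |
| 0.5% | 12.9% | 59% |

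**Table 5.** Four counts per arm make 16 combinations. The table has 15 rows, and the missing one is 0 v 0.

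**The case against.** The strongest reply is that the decision rarely turns on this. At 0 v 0 both upper limits (0% and 1.85%) are below 5%. Over all outcomes with at least one zero arm, the two methods give different verdicts with probability 0.26% at 2% v 2%, 0.12% at 0.5% in both arms, 1.4% at 1% v 0.5% and 2.1% at 2% v 1%. Coverage is poor only when low rates differ, and the plan also reports the rates by arm. All of this stands and limits the severity. It does not make a zero-width interval valid, and the high coverage at equal low rates partly reflects that a 0-to-0 interval contains a true difference of zero.

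RESPECT is also an imperfect guide. It was an arterial study with 6/7 Fr sheaths, and its list of major complications had no pulmonary embolism. This trial is venous, allows sheaths up to 12 Fr and counts any confirmed pulmonary embolism. Venous rates could be higher, so RESPECT's zeros make rates well below 1% possible, not established.

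Three stronger readings are not supported:
- A reader might infer a false signal of harm from 4 v 0, where the bootstrap excludes zero although Fisher's exact p is 0.12. The plan tests nothing on the lower limit. With equal true rates, that limit exceeds zero with probability 0.7% at 0.5% and 2.1% at 1% or 2%, below the nominal 2.5%.
- A reader might infer that 0 v 0 would produce a wrong non-inferiority claim. It would not.
- A reader might infer that the missing row undermines the power calculation. Table 5 serves to check Newcombe as an approximation for power, and a 0 v 0 row (1.85% v 0%) would support its conclusion that Newcombe is conservative.

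**Conclusion.** The point holds as a should-fix. As written, the only primary safety interval is 0% to 0% at 0 v 0, leaves out one arm's uncertainty when that arm has no events, and covers 63% to 86% at low unequal rates of 0.5% v 0.25% and 1% v 0.5%. At 5 v 0 the verdict depends on the method. At the planning assumption of 2% in both arms the bootstrap interval is adequate (96% coverage) and 0 v 0 is remote (0.03%). The problem becomes practical if true rates are well below 1%.

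These figures assume 204 limbs per arm, independent limbs, complete follow-up, and treatment received equal to treatment assigned. The zero-width result at 0 v 0 needs none of these assumptions.

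**What to change.** In 9.2.3, before any outcome data are seen, name the Newcombe interval as the primary safety confidence interval and keep the patient-level bootstrap as supportive. State the clustering adjustment in full. One option is to replace 204 by an effective 204/(1 + ρ) limbs per arm, where ρ is the within-patient correlation, with a fixed value of ρ for when it cannot be estimated. At 0 v 0 this ranges from ±1.85% (ρ = 0) to ±3.63% (ρ = 1, 102 per arm), both inside the margin. An adjustment is needed because in Table 5, with two patients having events in both legs, the bootstrap limit can exceed Newcombe's (4 v 2: 4.4% v 4.0%).

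At the least, name Newcombe as the reported interval whenever either arm has zero events, and say which interval then governs the decision. A trigger worded as few events would be undefined and data-dependent. Add the 0 v 0 row to Table 5.

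Cost: this changes analysis wording only; the sample size stays. If Newcombe governs the decision throughout, the probability of meeting non-inferiority at 2% v 2% is 0.88, the figure the plan already states, instead of about 0.95 with the bootstrap. At 2% v 1% it is 0.75 instead of 0.89. A clustering adjustment with ρ above zero would lower the Newcombe figures somewhat further.
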